#### MD part:

It is planned to include a total of 6 patients in this trial part. The planned sample size is not based on a power calculation but is in general considered as sufficient for the evaluation of multiple dose safety and pharmacokinetics of drugs with intravitreal route of administration.

## 8. INFORMED CONSENT, TRIAL RECORDS, DATA PROTECTION, PUBLICATION POLICY, AND ADMINISTRATIVE STRUCTURE

The trial will be carried out in accordance with the Medical Devices Directive (93/42/EEC) and the harmonised standards for Medical Devices (ISO 14155, current version).

The trial will be carried out in compliance with the protocol, the ethical principles laid down in the Declaration of Helsinki, in accordance with the ICH Harmonized Guideline for Good Clinical Practice (GCP), relevant BI Standard Operating Procedures (SOPs), the EU directive 2001/20/EC / EU regulation 536/2014 and other relevant regulations. Investigators and site staff must adhere to these principles. Deviation from the protocol, the principles of ICH GCP or applicable regulations as will be treated as “protocol deviation”.

Standard medical care (prophylactic, diagnostic and therapeutic procedures) remains the responsibility of the treating physician of the patient.

The investigator will inform the sponsor immediately of any urgent safety measures taken to protect the trial patients against any immediate hazard, as well as of any serious breaches of the protocol or of ICH GCP.

The Boehringer Ingelheim transparency and publication policy can be found on the following web page: [trials.boehringer-ingelheim.com](http://trials.boehringer-ingelheim.com). The rights of the investigator and of the sponsor with regard to publication of the results of this trial are described in the investigator contract. As per the project publication strategy, interim cohort data may be published as available, while full results will be published after CTR finalization. The certificate of insurance cover is made available to the investigator and the patients and is stored in the ISF.

### 8.1 TRIAL APPROVAL, PATIENT INFORMATION, INFORMED CONSENT

This trial will be initiated only after all required legal documentation has been reviewed and approved by the respective Institutional Review Board (IRB / Independent Ethics Committee (IEC and competent authority (CA) according to national and international regulations. The same applies for the implementation of changes introduced by amendments.

Prior to patient participation in the trial, written informed consent must be obtained from each patient (or the patient's legally accepted representative) according to ICH-GCP and to the regulatory and legal requirements of the participating country. Each signature must be personally dated by each signatory and the informed consent and any additional patient-information form retained by the investigator as part of the trial records. A signed copy of the informed consent and any additional patient information must be given to each patient or the patient's legally accepted representative.”

The investigator or delegate must give a full explanation to trial patients based on the patient information form. A language understandable to the patient should be chosen, technical terms and expressions avoided, if possible.

The patient must be given sufficient time to consider participation in the trial. The investigator or delegate obtains written consent of the patient's own free will with the informed consent form after confirming that the patient understands the contents. The investigator or his delegate must sign (or place a seal on) and date the informed consent form. If a trial collaborator has given a supplementary explanation, the trial collaborator also signs (or places a seal on) and dates the informed consent:

Re-consenting may become necessary when new relevant information becomes available and should be conducted according to the sponsor's instructions.

The consent and re-consenting process should be properly documented in the source documentation.

## **8.2 DATA QUALITY ASSURANCE**

A risk-based approach is used for trial quality management. It is initiated by the assessment of critical data and processes for trial subject protection and reliability of the results as well as identification and assessment of associated risks. An Integrated Quality and Risk Management Plan documents the rationale and strategies for risk management during trial conduct including monitoring approaches, vendor management and other processes focusing on areas of greatest risk.

Continuous risk review and assessment may lead to adjustments in trial conduct, trial design or monitoring approaches.

A quality assurance audit/inspection of this trial may be conducted by the sponsor, sponsor's designees, or by IRB / IEC or by regulatory authorities. The quality assurance auditor will have access to all medical records, the investigator's trial-related files and correspondence, and the informed consent documentation of this clinical trial.

## **8.3 RECORDS**

CRFs for individual patients will be provided by the sponsor. See [Section 4.1.5.2](#) for rules about emergency code breaks. For drug accountability, refer to [Section 4.1.8](#).

### **8.3.1 Source documents**

In accordance with regulatory requirements, the investigator should prepare and maintain adequate and accurate source documents and trial records that include all observations and other data pertinent to the investigation on each trial patient. Source data as well as reported data should follow the "ALCOA principles" and be **attributable, legible, contemporaneous, original and accurate**. Changes to the data should be traceable (audit trail).

Data reported on the CRF must be consistent with the source data or the discrepancies must be explained.

The current medical history of the patient may not be sufficient to confirm eligibility for the trial and the investigator may need to request previous medical histories and evidence of any diagnostic tests. In this case, the investigator must make at least one documented attempt to

retrieve previous medical records. If this fails, a verbal history from the patient, documented in their medical records, would be acceptable.

During the site visit the sponsor's Clinical Research Associate (CRA) or auditor must be granted access to copies of source documents (please see [Section 8.3.2](#)). Before sending or uploading those copies, the investigator must ensure that all patient identifiers (e.g. patient's name, initials, address, phone number, social security number) have properly been removed or redacted from any copy of the patients' source documents.

If the patient is not compliant with the protocol, any corrective action e.g. re-training must be documented in the patient file.

For the CRF, data must be derived from source documents, for example:

- Patient identification: gender, year of birth (in accordance with local laws and regulations)
- Patient participation in the trial (substance, trial number, patient number, date patient was informed)
- Dates of patient's visits, including dispensing of trial medication
- Medical history (including trial indication and concomitant diseases, if applicable)
- Medication history
- Adverse events and outcome events (onset date (mandatory), and end date (if available))
- Serious adverse events (onset date (mandatory), and end date (if available))
- Concomitant therapy (start date, changes)
- Originals or copies of laboratory results and other imaging or testing results, with proper documented medical evaluation (in validated electronic format, if available)
- Completion of patient's participation in the trial" (end date; in case of premature discontinuation document the reason for it).
- Prior to allocation of a patient to a treatment into a clinical trial, there must be documented evidence in the source data (e.g. medical records) that the trial participant meets all inclusion criteria and does not meet any exclusion criteria. The absence of records (either medical records, verbal documented feedback of the patient or testing conducted specific for a protocol) to support inclusion/exclusion criteria does not make the patient eligible for the clinical trial.

### **8.3.2 Direct access to source data and documents**

The sponsor will monitor the conduct of the trial by regular on-site monitoring visits and in-house data quality review. The frequency of site monitoring will be determined by assessing all characteristics of the trial, including its nature, objective, methodology and the degree of any deviations of the intervention from normal clinical practice.

The investigator/institution will allow site trial-related monitoring, audits, IRB / IEC review and regulatory inspections. Direct access must be provided to the CRF and all source documents/data, including progress notes, copies of laboratory and medical test results, which must be available at all times for review by the CRA, auditor and regulatory inspector (e.g. FDA). They may review all CRFs and informed consents. The accuracy of the data will be verified by direct comparison with the source documents described in [Section 8.3.1](#). The sponsor will also monitor compliance with the protocol and GCP.

An adaptive approach to clinical trial monitoring will be utilised. The sponsor will perform a risk assessment of the trial to determine the extent and nature of monitoring required in order to ensure the reliability and robustness of the results. Regular review of risk reports will provide sponsor oversight during trial conduct and direct monitoring activities to the areas of greatest risk which have the most potential impact to patient safety and data quality.

### 8.3.3 Storage period of records

#### Trial site(s):

The trial site(s) must retain the source and essential documents (including ISF) according to contract or the local requirements valid at the time of the end of the trial (whatever is longer).

#### Sponsor:

The sponsor must retain the essential documents according to the sponsor's SOPs.

## 8.4 EXPEDITED REPORTING OF ADVERSE EVENTS

BI is responsible to fulfil their legal and regulatory reporting obligation in accordance with regulatory requirements.

## 8.5 STATEMENT OF CONFIDENTIALITY AND PATIENT PRIVACY

Data protection and data security measures are implemented for the collection, storage and processing of patient data in accordance with the principles 7 and 12 of the WHO GCP handbook.

Individual patient data obtained as a result of this trial is considered confidential and disclosure to third parties is prohibited with the following exceptions:

Personalised treatment data may be given to the patient's personal physician or to other appropriate medical personnel responsible for the patient's welfare. Data generated at the site as a result of the trial need to be available for inspection on request by the participating physicians, the sponsor's representatives, by the IRB / IEC and the regulatory authorities.

## 8.6 TRIAL MILESTONES

The **start of the trial** is defined as the date when the first patient in the whole trial signs informed consent.

The **end of the trial** is defined as the date of the last visit of the last patient in the whole trial ("Last Patient Completed").

The "**Last Patient Last Treatment**" (LPLT) date is defined as the date on which the last patient in the whole trial is administered the last dose of trial treatment (as scheduled per protocol or prematurely). Individual investigators will be notified of SUSARs occurring with the trial medication until 30 days after LPLT at their site.

**Early termination of the trial** is defined as the premature termination of the trial due to any reason before the end of the trial as specified in this protocol.

**Temporary halt of the trial** is defined as any unplanned interruption of the trial by the sponsor with the intention to resume it.

**Suspension of the trial** is defined as an interruption of the trial based on a Health Authority request.

The IEC / competent authority in each participating EU member state will be notified about the trial milestones according to the respective laws.

A final report of the clinical trial data will be written only after all patients have completed the trial in all countries (EU or non-EU) to incorporate and consider all data in the report.

The sponsor will submit to the EU database a summary of the final trial results within one year from the end of a clinical trial as a whole, regardless of the country of the last patient (EU or non-EU).

## 8.7 ADMINISTRATIVE STRUCTURE OF THE TRIAL

The trial is sponsored by Boehringer Ingelheim (BI). A Coordinating Investigator is responsible to coordinate investigators at the different sites participating in this trial. Tasks and responsibilities are defined in a contract.

An extended SMC composed of participating investigators, members of the BI trial team and two trial independent external ophthalmological experts will be established for both SRD and MD parts. The primary responsibility of the SMC is to ensure and protect the safety and well-being of the patients participating in the trial. In the SRD part, the SMC will review individual and aggregated safety data at regular intervals to determine the safety profile and risk/benefit ratio and decide on the next dose level and the next cohort size, or the appropriacy of further enrolment. After completion of the SRD part, the SMC will decide on the selection of the highest dose established as safe and tolerable (during SRD part) and its continuing evaluation in the MD part of the trial.

Details of the SMC responsibilities and procedures are described in the SMC charter. Relevant documentation on the participating (Principal) Investigators (e.g. their curricula vitae) will be filed in the ISF. The investigators will have access to the BI clinical trial portal (Clinergize) to facilitate document exchange and maintain electronic ISF.

BI has appointed a Clinical Trial Leader (CT Leader), responsible for coordinating all required activities, in order to

- manage the trial in accordance with applicable regulations and internal SOPs,
- direct the clinical trial team in the preparation, conduct, and reporting of the trial,
- ensure appropriate training and information of Clinical Trial Managers (CT Managers), Clinical Research Associates (CRAs), and investigators of participating countries.

The organisation of the trial in the participating countries will be performed by the respective local or regional BI-organisation (Operating Unit, OPU) in accordance with applicable regulations and BI SOPs, or by a Contract Research Organisation (CRO) with which the responsibilities and tasks will have been agreed and a written contract filed before initiation of the clinical trial.

Data Management and Statistical Evaluation will be done by BI according to BI SOPs.

Tasks and functions assigned in order to organise, manage, and evaluate the trial are defined according to BI SOPs. A list of responsible persons and relevant local information can be found in the ISF.

A central laboratory service will be used in this trial. Details will be provided in Central Laboratory Manual, available in the ISF.

## 10. APPENDICES

### 10.1 INSTRUCTIONS FOR USE

Not applicable.

### 10.2 PHARMACOKINETIC METHODS AND ANALYSES

Not applicable.

### 10.3 TIME SCHEDULE FOR PHARMACOKINETIC (PK) BLOOD SAMPLING

Table 10.3: 1 Time schedule for PK and ADA blood sampling and ECG recording during SRD part

Course	Visit	Day	Planned Time	Planned Time [h]	PK BI 754312	ADA	ECG 
1	V2	1	Before drug administration of BI 754312	-0:30 	X	X	X
			Drug administration	0:00			
	V2	1	4h after drug administration	4:00 	X		X
	V3	4 (+/- 1 day)	3 days after drug administration	72:00	X		X
	V4	8 (+/- 1 days)	1 week after drug administration	168:00	X		X
	V5	15 (+/- 2 days)	2 weeks after drug administration	336:00	X	X	X
	V6	22 (+/- 2 days)	3 weeks after drug administration	504:00			
	V7	29 (+/- 2 days)	4 weeks after drug administration	672:00	X	X	X
	V8	56 (+/- 4 days)	8 weeks after drug administration	1344:00	X		
	V9	84 (+/- 4 days)	12 weeks after drug administration	2016:00	X		
End of trial	V10	100 (+/- 7 days)	14 weeks after drug administration	2352:00	X	X	X

(1) The -0:30 sample can be taken between 1h and 5min before drug administration.

(2) Time points are also required for sample identification.

(3) Time points with triplicate resting ECG, shortly before PK sampling.

(4) A time window of +/- 15 min for sample drawing is allowed here.

Table 10.3: 2 Time schedule for PK and ADA blood sampling and ECG recording during MD part

Course	Visit	Day	Planned Time [h]	Planned Time [h]	PK BI 754132	ADA	ECG 
1	V2	1	Before 1 st drug administration of BI 754132	-4:00 	X	X	X
			1 st drug administration	0:00			
	V3	29 (+/- 3 days)	Before 2 nd drug administration of BI 754132	671:55 	X		X
			2 nd drug administration	672:00			
	V4	57 (+/- 3 days)	Before 3 rd drug administration of BI 754132	1343:55 	X		X
			3 rd drug administration	1344:00			
Follow up period	V5	85 (+/- 7 days)	12 weeks after first drug administration	2016:00 	X	X	X
	V6	113 (+/- 7 day)	16 weeks after first drug administration	2688:00 	X		
End of Trial	V7	155 (+/- 7 day)	22 weeks after first drug administration	3360:00 	X	X	X

- (1) PK and ADA sampling as well as ECG measurement must be performed within 4 hours prior to the IVT drug administration, and each sampling and measurement timepoint has to be entered in the eCRF.
- (2) Time points are also required for sample identification.
- (3) Time points with triplicate resting ECG, shortly before PK sampling.

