#### 2.1.3 Secondary endpoint(s)

SRD part:

- Number of patients with drug-related AEs from drug administration until EOT
- Number of patients with any ocular AEs in the study eye from drug administration until EOT
- $C_{\max}$  (maximum serum concentration of BI 754132 after a single intravitreal dose)
- $AUC_{0-\infty}$  (area under the concentration-time curve of BI 754132 in serum over the time interval from 0 extrapolated to infinity)
- $t_{\max}$  (time from dosing to maximum serum concentration of BI 754132)

MD part:

- Systemic exposure of BI 754132 after multiple IVT doses by determination of  $C_{\min,1}$  and  $C_{\min,2}$  (trough levels before second and third administrations) and plasma concentrations 4, 8 and 14 weeks after the third administration

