For the MD part, the first patient will receive one dose and will be monitored after four weeks to exclude acute AEs and especially adverse changes of the optic disc. Data will be assessed by the dosing investigator and 2 representatives of the sponsor who are involved in the trial. The decision to continue will be based on pre-specified criteria and include certified gradings from the Central Reading Center (CRC). If no AEs or adverse changes of the optic disc are observed, the first patient can receive the second dose. The second patient can be dosed at least 7 days thereafter. The second to sixth patients will follow the same procedure as the first patient, with a safety review after 4 weeks. In addition, this safety review will include safety data from visit 4 of the previous patient (assessment 4 weeks after second injection) as well as all available safety data of the previous patients. Written minutes of this review are being distributed to all investigators participating in this trial part.

In all patients included in the MD part of the trial, safety and pharmacokinetics will be studied to 98 days after the last injection.

[figure not shown]

Figure 3.1: 2 Schematic representation of the sentinel dosing in the MD part

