## 5.3 DRUG CONCENTRATION MEASUREMENTS AND PHARMACOKINETICS

### 5.3.1 Assessment of pharmacokinetics

For the assessment of pharmacokinetics, blood samples will be collected at the time points indicated in [Flow Chart I](#) and [Flow Chart II](#). The actual sampling times will be recorded in the CRFs and used for determination of pharmacokinetic parameters. Sampling should be done at the timepoints listed in the flow-chart I and II and within 4 hours prior to the IVT drug administration. It is important to ensure that the exact time of the assessment of pharmacokinetics is recorded. Planned time points for systemic pharmacokinetic samples are listed in [Appendix 10.3](#).

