## 6. INVESTIGATIONAL PLAN

### 6.1 VISIT SCHEDULE

For visit schedule, refer to [Flow Chart I](#) and [Flow Chart II](#). The acceptable time windows for visits are given in [Flow Chart I](#) and [Flow Chart II](#). For planned individual plasma concentration sampling times, refer to [Appendix 10.3](#).

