**6.2.2.3 Follow-up period and trial completion of MD part**

Patients must continue to be followed according to the visit schedule (unless they withdraw consent for further follow-up) in order to collect data up to the end of the planned observation period. Unscheduled visits will be possible at the discretion of the investigator at any time for safety reason. The unscheduled visits may include any assessments considered necessary by the investigator. All unscheduled visits should be described and documented in the medical/source record. The investigator may decide to administer standard treatment for ocular inflammation during the follow-up period as deemed medically appropriate.

Visit 7/End of Trial:

The Visit 7/EOT will be performed 42 days after the Visit 6 (see [Flow Chart II](#)).

The Visit 7/EOT is the final visit and the trial completion page in the eCRF has to be entered.

Withdrawal of consent

If a patient is not willing to continue in the trial and wants to withdraw consent prior to the end of the trial, the investigator should offer the possibility to continue the trial without further treatment until Visit7/EOT. If patient disagrees to continue under these circumstances, Visit 6 should be scheduled as soon as possible, and also Visit 7/EOT should be performed to assess for safety.

If patient refuses to participate at a Visit 6 or Visit 7, the trial completion page of the eCRF has to be filled in.

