#### Exclusion of PK concentrations

The ADS ADPC (PK concentrations per time-point or per time-interval) contains column variables ACEX or ACEXCO indicating inclusion/exclusion (ACEX) of a concentration and an analysis flag comment (ACEXCO). Exclusion of a concentration depends on the analysis flag comment ACEXCO. For example, if ACEXCO is set to 'ALL CALC', the value will be excluded for all types of analyses based on concentrations. If ACEXCO is set to 'DESC STATS', the value will be excluded from descriptive evaluations per planned time point/time interval. If ACEXCO contains the addition 'TIME VIOLATION' or 'TIME DEVIATION', the value can be used for further analyses based on actual times. If ACEXCO is set to 'HALF LIFE', the value will be excluded from half-life calculation (and, as a consequence, any calculation that relies on  $\lambda_z$ ) only; the value is included for all other analyses.

Further details are given in BI-KMED-TMCP-MAN-0014 "Noncompartmental Pharmacokinetic / Pharmacodynamic Analyses of Clinical Studies" (5) and BI-KMED-TMCP- MAN-0010: "Description of Analytical Transfer Files and PK/PD Data Files" (11).

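### Protocol Table 10.3:2 gives the MD Visit 7 sample a planned time of 3360 h (20 weeks), although its own row and the rest of the plan put that visit at 22 weeks, which is 3696 h

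*Protocol*

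**What the plan says.** Table 10.3:2 in Protocol Appendix 10.3 lists the MD sampling times by visit, study day, a description in words and a planned time in hours from the first dose. For Visit 7 (end of trial) the day is 155 with a window of 7 days either side, the description is "22 weeks after first drug administration", and the planned time is 3360:00. Footnote 2, attached to that hour, reads "Time points are also required for sample identification".

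Other places fix the same visit:

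- Flow Chart II places Visit 7 at Day 155, Week 22, and Section 1.3 describes the MD part as lasting 22 weeks.
- Section 6.2.2.3: "The Visit 7/EOT will be performed 42 days after the Visit 6".
- Section 3.1: "safety and pharmacokinetics will be studied to 98 days after the last injection".
- Section 2.1.3 includes in the MD secondary endpoint "plasma concentrations 4, 8 and 14 weeks after the third administration". SAP Sections 5.2.2 and 7.5.2 keep the same three time points.

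The protocol directs readers to Appendix 10.3 for the planned times. Section 5.3.1 says "Planned time points for systemic pharmacokinetic samples are listed in" that appendix, and Section 6.1 says "For planned individual plasma concentration sampling times, refer to" it. The SAP (Section 7, on exclusion of PK concentrations) refers to "descriptive evaluations per planned time point/time interval".

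**The concern.** The hour in the Visit 7 row cannot hold together with the day and the week in the same row. A planned time is the label under which a concentration is identified, listed and summarised. If 3360 h passes from this table into the sample-identification scheme or the PK concentration dataset, two things could follow. The last of the three concentrations after the third dose could be reported at 20 weeks instead of 22, that is, 12 weeks after the third dose instead of the 14 named in the endpoint. Alternatively, samples drawn on the correct day could be queried as timing deviations. Neither is automatic, because the documents do not say that a departure from the nominal hour leads to exclusion.

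**Working it through.** **Conversions.** With the first dose at 0 h on Day 1, hours = (study day - 1) x 24, and hours = weeks x 168.

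**Check on the other MD rows.** Days and hours are from Table 10.3:2; weeks count from the first dose.

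| Visit | Day | (Day - 1) x 24 | Weeks x 168 | Printed hour |
|---|---|---|---|---|
| 3 (second dose) | 29 | 672 | 4 x 168 = 672 | 672 |
| 4 (third dose) | 57 | 1344 | 8 x 168 = 1344 | 1344 |
| 5 | 85 | 2016 | 12 x 168 = 2016 | 2016 |
| 6 | 113 | 2688 | 16 x 168 = 2688 | 2688 |
| 7 | 155 | 3696 | 22 x 168 = 3696 | **3360** |

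The conversions reproduce every hour except the one for Visit 7.

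**What 3360 h means.**

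- From the first dose: 3360 / 168 = 20 weeks; 3360 / 24 + 1 = Day 141.
- From the third dose: (3360 - 1344) / 168 = 12 weeks.
- From Visit 6: (3360 - 2688) / 24 = 28 days.

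**What the plan's other statements give for Visit 7.**

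1. Study day (table row and Flow Chart II): (155 - 1) x 24 = 3696 h.
2. Week (table row, Flow Chart II and Section 1.3): 22 x 168 = 3696 h.
3. 42 days after Visit 6 (Section 6.2.2.3): 2688 + 42 x 24 = 2688 + 1008 = 3696 h.
4. 98 days after the last injection (Section 3.1): 1344 + 98 x 24 = 1344 + 2352 = 3696 h.
5. 14 weeks after the third dose (Section 2.1.3): 1344 + 14 x 168 = 1344 + 2352 = 3696 h.

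The figure 3696 is printed nowhere in the documents; it follows from each of these statements.

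**Size.** 3696 - 3360 = 336 h, or two weeks. The window of Day 148 to Day 162 runs from (148 - 1) x 24 = 3528 h to (162 - 1) x 24 = 3864 h, so the printed hour lies 3528 - 3360 = 168 h before it opens.

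**Could it be a rounding convention?** In the single-dose table, Visits 8, 9 and 10 each differ by one day between study day and nominal hour. For example, Day 100 gives (100 - 1) x 24 = 2376 h against a printed 2352 h. Those differences of 24 h sit well inside their windows. A difference of 336 h, outside the window, is of another kind. Arithmetically, 3360 is Visit 6 plus one more four-week step (2688 + 672), whereas the interval to Visit 7 is six weeks.

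**Is it superseded text?** No. It stands in the current table. Amendment 6 changed this table, but its log mentions only the first pre-dose time and the footnotes.

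**The case against.** The strongest reply is that the error is real but has little effect.

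- The correct time can be read from two other cells in the row. Section 5.3.1 also tells sites to sample at the flow-chart time points, and Flow Chart II has Day 155.
- SAP Section 6.7 takes the acceptable visit windows from the flow charts, so visit adherence is judged against the right day.
- PK parameters are calculated from actual sampling times. The SAP allows a value flagged for a time violation or deviation to be used in analyses based on actual times.
- The endpoint is defined in words as 14 weeks after the third dose, and 3360 h does not appear in the SAP.
- No other row carries 3360 h, so the label is still unique and samples would not be confused with one another.
- The sample may be unquantifiable anyway. Section 1.2 reports systemic values in the 6 mg single-dose cohort within 4 to 168 h after injection.

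Most of this stands, and it limits the consequence to the nominal time label. It does not remove the contradiction. SAP Section 6.2 brings deviations in blood sampling times to the report planning and database lock meeting without naming the reference time, so a false query remains possible. A unique label can still be the wrong label in a summary by planned time. The point about quantifiability is an inference from single doses; accumulation over three doses is unknown, and the concentration belongs to the endpoint either way.

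**Conclusion.** The concern holds. The planned time of 3360 h for MD Visit 7 is wrong by 336 h, and the value consistent with the plan's other statements is 3696 h. It affects the nominal time of one of the five MD concentrations in the secondary endpoint (two troughs and three concentrations after the third dose), and the same row also schedules ADA and ECG. No visit, window, endpoint definition or PK parameter changes.

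The arithmetic rests only on counting from the first dose at 0 h on Day 1, which the other MD rows confirm. Any practical harm depends on whether the printed hour was carried into sample labels or dataset specifications, which the protocol and SAP do not show. The correction should be made, but the point does not threaten the trial's conclusions.

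**What to change.** In Table 10.3:2, change the Visit 7 planned time from 3360:00 to 3696:00. Then check that any sample-identification scheme or PK concentration data specification derived from the table uses 3696 h as the nominal time for Visit 7. If 3360 h has already been used there, correct it before concentrations are summarised by planned time. The cost is one figure in the table and that check; nothing changes for patients or sites.
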